2.2 Safety

The safety population is all subjects who received the single oral dose of study drug.

2.3 Pharmacokinetics

The pharmacokinetics valid population is all subjects who received the single oral dose and have no major protocol deviations affecting the PK variables and for whom the renal function group is assessable and who have a sufficient number of plasma concentrations to estimate the main PK parameters.

2.4 Included population

The included population is all screened subjects who are included in the study.

2.5 Screened population

The screened population is all subjects screened i.e. who signed the informed consent.

2.6 Primary population

The analyses of safety data will be performed based on the safety population. The analyses of PK will be performed on the PK population.

3 STATISTICAL METHODS**3.1 Statistical analysis strategy**

The statistical analyses will be performed in accordance with ICH E9 guideline and will be based on the pooled data from the individual study sites, unless otherwise stated.

Statistical analyses described in this document will be performed by Biotrial Biometrics, Rennes, France.

3.1.1 *Primary efficacy endpoint*

There is no efficacy assessment in this study.

3.1.2 *Secondary efficacy endpoint*

There is no efficacy assessment in this study.

3.1.3 Pharmacokinetic endpoints

The following PK plasma parameters for total telotristat ethyl, its active metabolite telotristat (LP-778902) and its inactive metabolite (LP-951757) will be derived by non-compartmental analysis of the plasma concentration-time profiles on Day 1 (pre-dose, 0.5, 1, 2, 3, 4, 6, 8, 12 hours post-dose), Day 2 (24 h), Day 3 (48 h) and Day 4 (72 h):

- C_{max} : Maximum observed plasma drug concentration
- t_{max} : Time to maximum observed plasma concentration
- AUC_{0-inf} : Area under the plasma concentration-time curve from time 0 to infinity calculated as follows:

$$AUC_{0-inf} = AUC_{0-tlast} + C_{last}/\lambda_z$$

with C_{last} as the last quantifiable concentration

- $AUC_{0-tlast}$: Area under the plasma concentration-time curve from 0 to time t corresponding to the last quantifiable concentration
- $t_{1/2}$: Apparent terminal elimination half-life calculated as follows:

$$t_{1/2} = \ln(2)/\lambda_z$$
- λ_z : Apparent first order terminal elimination rate constant
- CL/F : Apparent total clearance from plasma
- V_z/F : Apparent volume of distribution
- f_u : Unbound plasma fraction, there will be 4 replicates by timepoint.

For C_{max} and AUC , the following active metabolite/parent (i.e telotristat ethyl) and active metabolite (LP-778902)/[active metabolite+ telotristat ethyl] ratios (normalized and not normalized) will also be calculated:

- $MRC_{max} = (C_{max} \text{ LP-778902}) / (C_{max} \text{ telotristat ethyl})$
- $MRC_{maxNorm} = (C_{max} \text{ LP-778902/Molecular weight(MW)}_{LP-778902}) / (C_{max} \text{ telotristat ethyl/MW}_{telotristat ethyl})$
- $MRAUC_{0-inf} = (AUC_{0-inf} \text{ LP-778902}) / (AUC_{0-inf} \text{ telotristat ethyl})$
- $MRAUC_{0-infNorm} = (AUC_{0-inf} \text{ LP-778902/MW}_{LP-778902}) / (AUC_{0-inf} \text{ telotristat ethyl/MW}_{telotristat ethyl})$
- $MRAUC_{0-tlast} = (AUC_{0-tlast} \text{ LP-778902}) / (AUC_{0-tlast} \text{ telotristat ethyl})$
- $MRAUC_{0-tlastNorm} = (AUC_{0-tlast} \text{ LP-778902/MW}_{LP-778902}) / (AUC_{0-tlast} \text{ telotristat ethyl/MW}_{telotristat ethyl})$
- $MRC_{maxTotal} = (C_{max} \text{ LP-778902}) / (C_{max} \text{ LP-778902} + C_{max} \text{ telotristat ethyl})$
- $MRC_{maxTotalNorm} = (C_{max} \text{ LP-778902/MW}_{LP-778902}) / (C_{max} \text{ LP-778902/MW}_{LP-778902} + C_{max} \text{ telotristat ethyl/MW}_{telotristat ethyl})$
- $MRAUC_{0-infTotal} = (AUC_{0-inf} \text{ LP-778902}) / (AUC_{0-inf} \text{ LP-778902} + AUC_{0-inf} \text{ telotristat ethyl})$
- $MRAUC_{0-infTotalNorm} = (AUC_{0-inf} \text{ LP-778902/MW}_{LP-778902}) / (AUC_{0-inf} \text{ LP-778902/MW}_{LP-778902} + AUC_{0-inf} \text{ telotristat ethyl/MW}_{telotristat ethyl})$
- $MRAUC_{0-tlastTotal} = (AUC_{0-tlast} \text{ LP-778902}) / (AUC_{0-tlast} \text{ LP-778902} + AUC_{0-tlast} \text{ telotristat ethyl})$
- $MRAUC_{0-tlastTotalNorm} = (AUC_{0-tlast} \text{ LP-778902/MW}_{LP-778902}) / (AUC_{0-tlast} \text{ LP-778902/MW}_{LP-778902} + AUC_{0-tlast} \text{ telotristat ethyl/MW}_{telotristat ethyl})$

For the calculation of metabolic ratios (MR) for $AUC_{0-tlast}$, t_{last} for telotristat ethyl could be different from t_{last} for its active metabolite telotristat (LP-778902).

The amount of unchanged telotristat ethyl and its active metabolite telotristat (LP-778902) excreted in urine (A_e) will also be determined (where possible).

3.1.4 Protein binding endpoints

The unbound concentrations for telotristat ethyl, its active metabolite telotristat (LP-778902) and its inactive metabolite (LP-951757) will be derived at each time point available as follows : $C_u = C_{Total} * \text{mean}(f_u)$, where $\text{mean}(f_u)$ represents the mean of the unbound fractions by timepoint.

The following PK parameters for unbound telotristat ethyl and its active metabolite telotristat (LP-778902) will be calculated using the unbound fraction F_u (defined for each subject as the mean over all time points of the mean of f_u):

- C_{maxu} : Maximum plasma concentration calculated by: $C_{maxu} = C_{max} * F_u$
- AUC_{0-infu} : Area under the concentration-time curve unbound from 0 to infinity calculated by: $AUC_{0-infu} = AUC_{0-inf} * F_u$
- $AUC_{0-tlastu}$: AUC from 0 to the last quantifiable unbound concentration calculated by: $AUC_{0-tlastu} = AUC_{0-tlast} * F_u$
- CL_u/F : Apparent total clearance from plasma calculated by: $CL_u/F = CL/F * F_u$
- V_{zu}/F : Apparent volume of distribution calculated by: $V_{zu}/F = V_z/F * F_u$.

For C_{maxu} and AUC_u , the following MR (normalized and not normalized) will also be calculated:

- $MRC_{maxu} = (C_{maxu} \text{ LP-778902}) / (C_{maxu} \text{ telotristat ethyl})$
- $MRC_{maxuNorm} = (C_{maxu} \text{ LP-778902/Molecular weight(MW)}_{LP-778902}) / (C_{maxu} \text{ telotristat ethyl/MW}_{telotristat ethyl})$
- $MRAUC_{0-infu} = (AUC_{0-infu} \text{ LP-778902}) / (AUC_{0-infu} \text{ telotristat ethyl})$
- $MRAUC_{0-infuNorm} = (AUC_{0-infu} \text{ LP-778902/MW}_{LP-778902}) / (AUC_{0-infu} \text{ telotristat ethyl/MW}_{telotristat ethyl})$
- $MRAUC_{0-tlastu} = (AUC_{0-tlastu} \text{ LP-778902}) / (AUC_{0-tlastu} \text{ telotristat ethyl})$
- $MRAUC_{0-tlastuNorm} = (AUC_{0-tlastu} \text{ LP-778902/MW}_{LP-778902}) / (AUC_{0-tlastu} \text{ telotristat ethyl/MW}_{telotristat ethyl})$
- $MRC_{maxuTotal} = (C_{maxu} \text{ LP-778902}) / (C_{maxu} \text{ LP-778902} + C_{maxu} \text{ telotristat ethyl})$
- $MRC_{maxuTotalNorm} = (C_{maxu} \text{ LP-778902/MW}_{LP-778902}) / (C_{maxu} \text{ LP-778902/MW}_{LP-778902} + C_{maxu} \text{ telotristat ethyl/MW}_{telotristat ethyl})$
- $MRAUC_{0-infuTotal} = (AUC_{0-infu} \text{ LP-778902}) / (AUC_{0-infu} \text{ LP-778902} + AUC_{0-infu} \text{ telotristat ethyl})$
- $MRAUC_{0-infuTotalNorm} = (AUC_{0-infu} \text{ LP-778902/MW}_{LP-778902}) / (AUC_{0-infu} \text{ LP-778902/MW}_{LP-778902} + AUC_{0-infu} \text{ telotristat ethyl/MW}_{telotristat ethyl})$
- $MRAUC_{0-tlastuTotal} = (AUC_{0-tlastu} \text{ LP-778902}) / (AUC_{0-tlastu} \text{ LP-778902} + AUC_{0-tlastu} \text{ telotristat ethyl})$
- $MRAUC_{0-tlastuTotalNorm} = (AUC_{0-tlastu} \text{ LP-778902/MW}_{LP-778902}) / (AUC_{0-tlastu} \text{ LP-778902/MW}_{LP-778902} + AUC_{0-tlastu} \text{ telotristat ethyl/MW}_{telotristat ethyl})$

3.1.5 *Safety endpoints*

The safety endpoints are:

- AEs;
- Clinical safety endpoints: physical examination, vital signs, 12-lead ECGs;
- Clinical laboratory tests: haematology, coagulation, biochemistry, urinalysis;
- Pregnancy tests at screening, Day -1 and EOS/ Early discontinuation visit.

3.1.6 *Multiplicity*

A multiplicity correction will be used in the statistical analysis to compare renal impaired function groups to the healthy group. A Bonferroni procedure will be used to keep the overall type 1 error equals to 10%. For each test, the statistical level of significance will be 10% divided by the number of hypotheses tested.

3.1.7 *Significance testing and estimation*

A 90% confidence interval (CI) will be calculated for the geometric least square mean ratios from the analysis of the variance (ANOVA) on the log transformed C_{max} , AUC_{0-inf} and $AUC_{0-tlast}$ to illustrate the difference between renal impaired group versus the control group with normal renal function. If the data permitted, 90% CI will also be calculated for PK parameters of the unbound fractions.

Moreover, 90% CI of the median difference for t_{max} will be produced using Hodges-Lehmann estimation.

The statistical analysis of safety is only descriptive therefore no formal statistical significance testing will be performed.

3.2 **Analysis methods**

3.2.1 *Efficacy*

Not applicable.

3.2.2 *Pharmacokinetics*

The PK analysis will be performed by a non-compartmental approach using Phoenix[®] WinNonLin[®] version 7.0 (Pharsight) and will be performed on the PK population.

3.2.2.1 *PK parameters calculation*

The Ipsen PDM (Pharmacokinetics Drug Metabolism) instructions (version dated 20JUN2014) for PK parameters calculation will be followed.

The following rules will be used:

- Actual sampling times will be used for deriving PK parameters.
- If an entire concentration-time profile is below the limit of quantification (BLQ), the profile will be excluded from the PK analysis
- For plasma concentrations: all BLQ values occurring before C_{max} will be replaced by 0, the first BLQ concentration after C_{max} will be replaced by LOQ/2 and the following BLQ concentrations after C_{max} will be treated as missing.
- A non-BLQ data after 2 BLQ data or a BLQ data between 2 measurable concentrations will be treated as missing.
- If the pre-dose concentration is $\leq 5\%$ of the C_{max} value for a particular subject, that subject's data without baseline correction can be included in all PK and statistical analysis. If the pre-dose value is $> 5\%$ of C_{max} , descriptive statistics will be reported with and without the specific concerned subject(s).

- If the percentage of extrapolated part of $AUC_{0-\infty}$ exceeds 20% of $AUC_{0-\infty}$, the value of $AUC_{0-\infty}$ is not reported.
- All estimations of λ_z will be determined using at least the three last measurable concentration data (excluding the C_{max}) and over a time interval equal to at least 2 times the estimated elimination half-life ($t_{1/2}$). Moreover, only those data points judged to describe the terminal log-linear decline resulting in an adjusted coefficient of determination value > 0.7 will be used in the regression. If at least one of these 3 conditions is not fulfilled λ_z will be flagged. If λ_z is flagged, the derived parameters ($t_{1/2}$, $AUC_{0-\infty}$...) are flagged accordingly.
- The AUC will be estimated using lin/log trapezoidal rule with at least 4 measurable concentrations including at least 3 consecutive time points.
- AUC of a subject should represent more than 5% of the geometric mean AUC for each renal function group. If not, the subject is considered to have a very low plasma concentration and is not included in the calculation of descriptive statistics. However, concentrations for that subject will be reported in the appendix of the report.
- If the conditions on PK parameters detailed above are not fulfilled, unreliable PK parameters will be flagged in listings and excluded from the analysis.

Following oral administration of telotristat etiprate, absorption of telotristat ethyl was rapid and it was almost completely converted to the active metabolite telotristat (LP-778902). Therefore, as reported in the previous studies, some PK parameters for telotristat ethyl may not be calculated due to the telotristat ethyl concentrations being under the Limit of Quantification (LOQ).

No quantitative exposure data are available yet on the inactive metabolite (LP-951757) after oral administration of telotristat etiprate in humans. From the mass-balance study in humans, around 10% of the inactive metabolite (LP-951757) are retrieved in plasma from the initial amount of telotristat etiprate. Therefore, some LP-951757 concentrations may be under the LLOQ, making the estimation of the corresponding PK parameters difficult.

3.2.2.2 *Descriptive statistics and listings*

Descriptive summaries for each renal function group (arithmetic means, Standard Deviation (SD), Coefficient of Variation (CV%), geometric mean, geometric CV%, median, minimum, maximum, n and missing) of the plasma concentrations are calculated only if at least 2/3 of the data are above LOQ. If not, only minimum and maximum are reported.

For descriptive statistics on concentration data, the following rules will be followed:
For BLQ concentrations before C_{max} :

- If at least 2/3 of values are either BLQ values replaceable by zero and/or numeric values: statistics will be calculated considering replaceable and numeric values.
- If more than 1/3 of values are BLQ values not replaceable by zero (i.e. subjects for whom all values are BLQ): mean (SD) will not be calculated and considered as BLQ. Minimum (BLQ) and maximum value will be presented.

For BLQ concentrations after C_{max} :

- If at least 2/3 of values are not BLQ: statistics will be calculated with BLQ values replaced by the numerical value (LOQ/2).

- If more than 1/3 of values are BLQ: mean (SD) will not be calculated and considered as BLQ. Minimum (BLQ) and maximum value will be presented.

Descriptive summaries (arithmetic mean, SD, CV%, geometric mean, geometric CV%, median, minimum, maximum, n and missing) of the PK parameters will be presented by renal function group. Only median, [Min-Max] and n will be reported for t_{max} .

The descriptive statistics on the PK parameters will be calculated only if at least 2/3 of the data are well determined. Otherwise only minimum and maximum values will be reported.

All concentrations below LOQ or missing data will be labelled as such in the concentration data listings.

In case of outliers, two analyses will be performed: one considering the outliers and one excluding the outliers.

All listings will be sorted by renal function group, subject and measurement time.

3.2.2.3 *Graphical representations*

The following rules for plasma concentration versus time graphic representation will be used:

- No graphic representation will be made if all values are BLQ.
- BLQ values occurring before C_{max} will be replaced by “0”.
- The first BLQ concentration after C_{max} will be replaced by LOQ/2 and the following BLQ concentrations after C_{max} will be treated as missing.

Nominal times are to be used to display the concentration plots.

The graphic representation of PK parameters will be made only if at least 2/3 of the data are well determined.

3.2.2.4 *Statistical analyses*

3.2.2.4.1 *Plasma pharmacokinetics*

For each of the 3 analytes, listings with plasma concentrations (including PK blood sampling dates and times), plasma PK parameters and metabolic ratios will be provided by renal function group and subject.

Descriptive statistics on plasma concentrations of telotristat ethyl, its active metabolite telotristat (LP-778902) and its inactive metabolite (LP-951757) will be computed for each renal function group, overall and by gender.

The individual plasma concentration-time profiles of telotristat ethyl, its active metabolite telotristat (LP-778902) and its inactive metabolite (LP-951757) will be presented graphically on linear and log/linear coordinates for each renal function group in a separated graph, using different colors for males and females. Graph of arithmetic mean ($\pm SD$) on linear and log/linear coordinates will be presented with all renal function groups on the same graph and also for each renal function group by gender. All graphs will be presented on scales 0-24 h and 0-72 h.

Descriptive statistics on PK parameters and metabolic ratios for telotristat ethyl, its active metabolite telotristat (LP-778902) and its inactive metabolite (LP-951757) will be computed for each renal function group, overall and by gender.

Scatter plots and box-whisker plots will be presented for the comparison of C_{max} , $AUC_{0-tlast}$ and AUC_{0-inf} of renal function groups versus healthy control group, overall and by gender.

Additionally, for each of the 3 analytes, a linear-linear plot will be performed for C_{max} , AUC_{0-inf} and $AUC_{0-tlast}$, with individual PK parameters (y-axis) versus the respective individual estimated GFR value at baseline (x-axis). All subjects will be on the same graph.

An ANOVA will be performed separately for each renal impaired function group on the natural log-transformed C_{max} , $AUC_{0-tlast}$ and AUC_{0-inf} for both telotristat ethyl and its active metabolite with renal function group as a fixed term. Geometric mean ratios and corresponding 90% CI for each renal impaired group (Test) versus the healthy control group (Reference) will be computed using the following sample SAS code:

```
proc mixed data=ADPP;
  where=<Renal function group> in (Healthy Severe
    /* (Healthy Moderate) (Healthy Mild) */);
  model log(AVAL) = <Renal function group>;
  lsmeans <Renal function group> / cl alpha=0.10/<nb of hypotheses>;
  estimate "Renal impaired / Healthy" <Renal function group> -1 1 / cl
  alpha=0.10/<nb of hypotheses>;
run;
```

The resulting least-squares (LS) means, difference in LS means between two groups (test minus reference), and corresponding 90% CIs will be exponentiated. The exponentiation of the difference in LS means will yield the estimated ratio of the PK parameter for a renal impaired function group relative to healthy subjects. These ratios will be expressed as a percentage relative to the reference group (test [mild, moderate, or severe renal impaired groups] versus reference [healthy group]).

For each test, a Bonferroni correction will be applied to adjust the statistical level of significance in order to keep the overall type 1 error equals to 0.10 (see section 3.1.6 for details).

No analysis will be performed if more than 1/3 of the values are not determined.

In case of exclusion of subjects in the severe renal impaired function group or in the healthy group, a sensitivity ANOVA will be performed with the included subjects and only including their matching subjects.

For t_{max} , an estimate of the median difference and 90% CI of the median difference will be provided using Hodges-Lehmann estimation, based on Walsh averages, using the following SAS code:

```
proc npar1way hl alpha=0.1 data= ADPP;
  where <Renal function group> in (Severe Healthy) and
    PARAMCD='TMAX';
  class <Renal function group>;
  var AVAL;
  exact hl;
run;
```

The Wilcoxon-Mann-Whitney test will be used to test for the difference in t_{max} between healthy subjects and each renal function group.

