1.4 Clinical Data

Xermelo® (telotristat etiprate) has a marketing authorisation for the treatment of carcinoid syndrome diarrhoea in combination with SSA therapy in adults inadequately controlled by SSA therapy. Marketing authorisation was based on the results of clinical trials (11) (12) (13) during which over 230 subjects with carcinoid syndrome were treated with telotristat etiprate.

From a PK perspective, telotristat ethyl and its active metabolite (telotristat) have been characterised in healthy volunteers and subjects with carcinoid syndrome. Following oral administration of telotristat etiprate, telotristat ethyl is rapidly absorbed and extensively converted to its active metabolite (telotristat), with some conversion of telotristat to an inactive

metabolite LP-951757 CCI [REDACTED] [REDACTED] [REDACTED] [REDACTED]. Plasma concentrations of telotristat ethyl are significantly lower (approximately 100-fold lower) than those of its active metabolite (telotristat) in both healthy subjects and subjects with carcinoid syndrome at all dose levels investigated during clinical development.

Both telotristat ethyl and its active metabolite (telotristat) are highly bound to human plasma proteins (>99%). During previous investigations on clinical samples from healthy volunteers, the unbound fraction of the telotristat ethyl was below the limit of quantification and could not be assessed, while the unbound fraction of the active metabolite (telotristat) was estimated to be 0.356% (14). The estimated apparent total volume of distribution for telotristat is 296 L in healthy subjects and 231 L in subjects with carcinoid syndrome, which may be suggestive of tissue distribution.

In a [¹⁴C]-telotristat etiprate mass balance study in healthy subjects (15), reported values of cumulative excretion showed that approximately 93% of the administered dose of total radioactivity was recovered in the urine and faeces by the end of sample collection (240 h), with the majority (92.78%) of the dose being recovered from faeces and <1% recovered from the urine.

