8 PHARMACOKINETIC ASSESSMENTS

Detailed procedures for the collection, processing, labelling, storage, shipment and destruction of the samples will be provided in stand-alone documents (laboratory manual, PK sample management plan).

Pharmacokinetic blood samples will be collected predose (time 0) and up to 72 hours postdose. Sampling timepoints are presented in the study schedule of assessments in [Section 18.1](#).

Urine samples will be collected predose, and up to 72 hours postdose. Collection intervals are presented in the study schedule of assessment in [Section 18.1](#).

Plasma and urine concentrations of telotristat ethyl and its active metabolite (telotristat) will be determined by validated liquid chromatography/tandem mass spectrometry (LC-MS/MS) methods.

The following PK parameters for total telotristat ethyl, its active metabolite (telotristat) and the inactive metabolite LP-951757, will be determined (where possible):

- C_{\max} Maximum plasma concentration
- AUC_{inf} Area under the concentration-time curve (AUC) from 0 to infinity
- $AUC_{0-t_{\text{last}}}$ AUC from 0 to the last quantifiable concentration
- t_{\max} Time to maximum plasma concentration
- $t_{1/2}$ Apparent terminal elimination half life
- λ_z Apparent first order terminal elimination rate constant
- CL/F Apparent total clearance from plasma
- V_z/F Apparent volume of distribution
- f_u Unbound plasma fraction

The amount of unchanged telotristat ethyl and its active metabolite (telotristat) excreted in urine (A_e) will also be determined (where possible).

The ratio active metabolite (telotristat)/telotristat ethyl and the ratio active metabolite (telotristat)/[telotristat ethyl + active metabolite (telotristat)] will also be determined for C_{\max} and AUC.

The mean fraction f_u will be used to derive the following PK parameters for unbound telotristat ethyl and its active metabolite (telotristat):

- C_{\max} Maximum plasma concentration
- AUC_{inf} Area under the concentration-time curve (AUC) from 0 to infinity
- $AUC_{0-t_{\text{last}}}$ AUC from 0 to the last quantifiable concentration
- CL/F Apparent total clearance from plasma
- V_z/F Apparent volume of distribution

Protein binding

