11.4.5 Interim Analyses

There will be an interim analysis of PK and safety data following the completion of subjects with severely impaired renal function and demographically-matched healthy subjects with normal renal function (Part A) to determine whether subjects with mildly, and moderately impaired renal function (Part B) will be enroled in the study.

The decision to dose eight subjects with mildly impaired renal function and eight subjects with moderately impaired renal function will be based on the PK evaluation of the Part A subjects and the observation of a 2-fold increase in total and unbound fraction of either the maximal plasma concentration (C_{max}) or plasma exposure (AUC) of the active metabolite telotristat.

Decision will not be based on the PK evaluation of the telotristat ethyl since it is rapidly converted to its active metabolite, but also because its PK profile might not be fully characterised because of anticipated low (or below limit of quantification) plasma concentrations.

This 2-fold increase in total and unbound fraction of either the C_{max} or AUC of the active metabolite (telotristat) in subjects with severely impaired renal function as compared to healthy subjects with normal renal function is a clinically relevant increase and considered as a conservative approach for further PK investigations in subjects with mildly and moderately impaired renal function.

Indeed, in a previous study in healthy subjects (20), 250 mg telotristat etiprate given as a tablet led to a mean maximal plasma concentration (C_{max}) of 449 ng/mL (corresponding to 1.60 ng/mL unbound C_{max} based on an f_u of 0.356%) and a mean plasma exposure (AUC_{inf}) of 1305 h.ng/mL of the active metabolite (telotristat) (corresponding to 4.65 h.ng/mL unbound AUC based on an f_u of 0.356%) (see [Table 2](#) below).

A 2-fold increase in total and unbound fraction of either the mean C_{max} or AUC of the active metabolite (telotristat) would lead to approximately 900 ng/mL (corresponding to 6.40 ng/mL unbound C_{max} based on a 2-fold increase f_u of 0.712%) and 2600 h.ng/mL (corresponding to 18.51 h.ng/mL unbound AUC based on a 2-fold increase f_u of 0.712%) respectively. This mean plasma concentration is close to the one reported following a single oral dose of 1500 mg of telotristat etiprate (given to healthy subjects as six 250-mg tablets) from a previous study (21), while the exposure is below:

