3.2.2.4.3 Protein binding

Listings with unbound plasma concentrations (including unbound plasma fraction and PK blood sampling dates and times), unbound plasma PK parameters and metabolic ratios will be provided by renal function group and subject.

Descriptive statistics on plasma unbound concentrations of telotristat ethyl, its active metabolite telotristat (LP-778902) and its inactive metabolite (LP-951757) will be computed for each renal function group, overall and by gender.

Descriptive statistics on unbound PK parameters (including unbound fractions) and metabolic ratios for telotristat ethyl, its active metabolite telotristat (LP-778902) and its inactive metabolite (LP-951757) will be computed for each renal function group, overall and by gender.

Scatter plots and box-whisker plots will be presented for the comparison of C_{maxu} , $AUC_{0-tlastu}$, AUC_{0-inf} and unbound fractions of renal function groups versus healthy control group, overall and by gender.

If the data permitted, same ANOVA as above will be performed separately for each renal impaired function group on the natural log-transformed C_{maxu} , $AUC_{0-tlastu}$, AUC_{0-inf} and unbound fractions (fu; no log-transformed) for both telotristat ethyl and its active metabolite with renal function group as a fixed term. The same SAS code as the previous analysis will be used. Sensitivity analysis will also be conducted, the same method as described above will be used.

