14.2.3 DERIVED UNBOUND PHARMACOKINETIC DATA

Table 14.2.3.1.1: Telotristat Ethyl Unbound Plasma Concentrations (unit) (Summary Statistics) – Pharmacokinetic Population

Table 14.2.3.1.2: LP-778902 Unbound Plasma Concentrations (unit) (Summary Statistics) – Pharmacokinetic Population

SAP Final Version 2.0: 04 June 2018				41/43
Table	14.2.3.1.3:	LP-951757 Unbound Plasma Concentrations (unit) (Summary Statistics) – Pharmacokinetic Population		
Table	14.2.3.2.1:	Telotristat Ethyl Unbound Pharmacokinetic Parameters and Unbound Fractions (Summary Statistics) – Pharmacokinetic Population		
Table	14.2.3.2.2:	LP-778902 Unbound Pharmacokinetic Parameters and Unbound Fractions (Summary Statistics) – Pharmacokinetic Population		
Table	14.2.3.2.3:	LP-951757 Unbound Pharmacokinetic Parameters and Unbound Fractions (Summary Statistics) – Pharmacokinetic Population		
Table	14.2.3.2.4:	Metabolic Ratios for Unbound Pharmacokinetic Parameters (Summary Statistics) – Pharmacokinetic Population		
Figure	14.2.3.3.1:	Scatter Plots of C_{maxu} , $AUC_{0-tlastu}$, AUC_{0-inf} and unbound fractions for Telotristat Ethyl – Pharmacokinetic Population		
Figure	14.2.3.3.2:	Scatter Plots of C_{maxu} , $AUC_{0-tlastu}$, AUC_{0-inf} and unbound fractions for LP-778902 – Pharmacokinetic Population		
Figure	14.2.3.3.3:	Scatter Plots of C_{maxu} , $AUC_{0-tlastu}$, AUC_{0-inf} and unbound fractions for LP-951757 – Pharmacokinetic Population		
Figure	14.2.3.4.1:	Box-Whisker Plots of C_{maxu} , $AUC_{0-tlastu}$, AUC_{0-inf} and unbound fractions for Telotristat Ethyl – Pharmacokinetic Population		
Figure	14.2.3.4.2:	Box-Whisker Plots of C_{maxu} , $AUC_{0-tlastu}$, AUC_{0-inf} and unbound fractions for LP-778902 – Pharmacokinetic Population		
Figure	14.2.3.4.3:	Box-Whisker Plots of C_{maxu} , $AUC_{0-tlastu}$, AUC_{0-inf} and unbound fractions for LP-951757 – Pharmacokinetic Population		
Table	14.2.3.5.1.1:	Comparison of C_{maxu} , $AUC_{0-tlastu}$, AUC_{0-inf} and unbound fractions for Telotristat Ethyl between each Renal Impairment Group and Healthy Control Group (ANOVA) – Pharmacokinetic Population		
Table	14.2.3.5.1.2:	Comparison of C_{maxu} , $AUC_{0-tlastu}$, AUC_{0-inf} and unbound fractions for Telotristat Ethyl between each Renal Impairment Group and Healthy Control Group (ANOVA) – Sensitivity analysis – Pharmacokinetic Population		

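### SAP 3.1.4 multiplies CL/F and Vz/F by the unbound fraction where its own unbound-AUC formula requires division, so the tabulated unbound clearance and volume are wrong by a factor of Fu squared

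*SAP*

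**What the plan says.** SAP 3.1.4 derives five unbound parameters for telotristat ethyl and telotristat from the total-drug parameters and a per-subject mean unbound fraction, Fu. All five are obtained by multiplying by Fu:

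- Cmaxu = Cmax × Fu and AUC0-tlastu = AUC0-tlast × Fu
- AUC0-infu = AUC0-inf × Fu ("Area under the concentration-time curve unbound from 0 to infinity calculated by")
- CLu/F = CL/F × Fu ("Apparent total clearance from plasma calculated by")
- Vzu/F = Vz/F × Fu ("Apparent volume of distribution calculated by")

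Protocol section 8 says the mean unbound fraction "will be used to derive the following PK parameters for unbound telotristat ethyl and its active metabolite (telotristat"), and its list includes CL/F and Vz/F, but it gives no formulas. SAP Appendix 1, item 10, covers unbound concentrations only.

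SAP 3.2.2.4.3 plans "Descriptive statistics on unbound PK parameters (including unbound fractions) and metabolic ratios" by renal function group. Appendix 2 carries this into Tables 14.2.3.2.1 and 14.2.3.2.2 (the latter titled "LP-778902 Unbound Pharmacokinetic Parameters and Unbound Fractions (Summary Statistics")) and Listings 16.2.5.10.1 and 16.2.5.10.2.

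**The concern.** Exposure and clearance move in opposite directions. If unbound AUC is total AUC scaled down by Fu, unbound clearance must be total clearance scaled up by 1/Fu. The SAP scales both down.

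If Fu were the same in every group this would be only an error of scale. But whether renal impairment alters protein binding is a secondary objective of the study. If Fu differs between groups, the contrast in unbound clearance and volume is distorted, and it can point the wrong way. A reader would then find in one table an unbound AUC and an unbound clearance that contradict each other, in a study meant to inform dose recommendations in renal impairment.

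**Working it through.** **Inputs**

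- Dose: 250 mg telotristat ethyl (protocol 6.1), used without molecular-weight adjustment.
- Telotristat mean AUCinf, 250 mg tablet: 1305 h.ng/mL (protocol 11.4.5 and Table 2).
- Telotristat λz: 0.2140 per hour (protocol Table 2, tablet).
- Unbound fraction of telotristat: 0.356%, i.e. 0.00356 (protocol 1.4), and 0.712% in the doubled case (protocol 11.4.5).
- Apparent volume of telotristat in healthy subjects: 296 L (protocol 1.4).
- Assumed, because the SAP does not state them: CL/F = Dose/AUC0-inf and Vz/F = (CL/F)/λz.

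**Step 1. Reproduce the protocol's unbound figures.** Using unbound = total × fu:

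- 449 × 0.00356 = 1.60 ng/mL (stated 1.60)
- 1305 × 0.00356 = 4.65 h.ng/mL (stated 4.65)
- 2600 × 0.00712 = 18.51 h.ng/mL ("corresponding to 18.51 h.ng/mL unbound AUC based on a 2-fold increase" in fu)
- 12634 × 0.00356 = 44.98 h.ng/mL (stated 44.98)

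The protocol therefore supports the SAP's AUC0-infu line. The clearance and volume lines are the ones that must change.

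**Step 2. Algebra.**

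- CLu/F = Dose/AUC0-infu = Dose/(AUC0-inf × Fu) = (CL/F)/Fu.
- Vzu/F = (CLu/F)/λz = (Vz/F)/Fu.
- SAP value ÷ consistent value = Fu² for both.
- Under the SAP, CLu/F × AUC0-infu = Dose × Fu². With the figures above that is 250 mg × 0.00356² = 0.0032 mg, not 250 mg.

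**Step 3. Size for telotristat.** CL/F = 250,000,000 ng ÷ 1305 h.ng/mL = 191.6 L/h.

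| Quantity | SAP formula | Consistent formula |
|---|---|---|
| CLu/F | 191.6 × 0.00356 = 0.68 L/h | 191.6 ÷ 0.00356 ≈ 53,800 L/h |
| Vzu/F from 296 L | 1.05 L | about 83,100 L |
| Vzu/F from 191.6 ÷ 0.2140 = 895 L | 3.19 L | about 251,500 L |

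Dividing the dose by the protocol's own unbound AUC of 4.65 gives 53,763 L/h, which agrees with the consistent value apart from rounding. The error factor is the same in every row: 1/0.00356² = 78,904. At fu = 0.712% it is 1/0.00712² = 19,726.

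For telotristat ethyl no factor can be computed, because in earlier work "the unbound fraction of the telotristat ethyl was below the limit of quantification and could not be assessed". With binding above 99% (protocol 1.4), it exceeds 1/0.01² = 10,000.

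**Step 4. Effect on the contrast between groups.** The SAP ratio is (CL/F ratio) × (Fu ratio). The consistent ratio is (CL/F ratio) ÷ (Fu ratio). Their quotient is the Fu ratio squared:

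| Fu,test/Fu,ref | Distortion of ratio |
|---|---|
| 1.0 | none |
| 1.1 | 1.21 |
| 1.25 | 1.56 |
| 1.5 | 2.25 |
| 2.0 | 4.0 |

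- *Fu doubles, CL/F unchanged.* The SAP value doubles (0.68 to 1.36 L/h); the consistent value halves (53,812 to 26,906 L/h). The direction is reversed.
- *Protocol 11.4.5 illustration (total AUC and fu both doubled).* CL/F = 250,000,000 ÷ 2600 = 96.15 L/h. The SAP gives 96.15 × 0.00712 = 0.68 L/h, unchanged. The consistent value is 250,000,000 ÷ 18.51 = 13,506 L/h, a ratio to 53,763 of 0.25.

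The squared factor is exact for individual subjects and for geometric means. For arithmetic means it is approximate, but a simulation with a 2-fold Fu ratio and a between-subject CV of Fu of 10% or 30% gave 4.00 in both cases.

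**The case against.** **The reach is narrow.** SAP 3.2.2.4.3 limits the unbound ANOVA to Cmaxu, AUC0-tlastu, AUC0-infu and the unbound fraction, and the Part B trigger uses Cmax or AUC. No test/reference ratio is planned for CLu/F or Vzu/F; a reader would have to form one from descriptive tables. For telotristat ethyl, SAP 3.2.2.2 would leave only the minimum and maximum if fewer than two thirds of the values are well determined, so in practice the error may matter for one analyte. All of this stands, and it keeps the point out of the inferential results.

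**The absolute values are illustrations.** They divide a parent dose by a mean metabolite AUC, and the two volume inputs (296 L and 895 L) differ. That also stands. The error factor 1/Fu² and the ratio distortion do not depend on the dose basis, the molecular weight or the volume chosen.

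**Another document may hold the right formula.** SAP 3.2.2.1 says the sponsor's internal PK instructions will be followed, and these are not available here. They cannot be presumed to override an explicit SAP formula, but the consequence should be read as applying if the SAP is programmed as written. The quality control in SAP 4.3 looks for nonsensical results and might question 0.68 L/h. It also checks agreement with the SAP, and a faithfully coded formula would pass that check.

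**It could be a misread character.** This is unlikely: both lines carry the same operator, and the neighbouring lines read correctly.

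**Conclusion.** The formulas for CLu/F and Vzu/F are wrong as written. They contradict the AUC0-infu formula in the same list, which the protocol's worked figures confirm. The reported values would be too low by 1/Fu² (78,904-fold for telotristat at 0.356%). Any between-group comparison would be off by the square of the Fu ratio: nothing if binding is equal, 4-fold if Fu doubles, with reversal of direction possible.

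The conclusion rests on one assumption, the standard non-compartmental definitions of CL/F and Vz/F. Nothing in either document suggests another.

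Cmaxu and the unbound AUCs scale in the right direction and are unaffected, as are the unbound metabolic ratios built on them, all ANOVAs and the Part B decision. This should be fixed before the unbound tables are produced, but it does not threaten the primary comparison.

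**What to change.** In SAP 3.1.4, write CLu/F = (CL/F)/Fu and Vzu/F = (Vz/F)/Fu, and state that Fu enters as a fraction, not a percentage. Write out CL/F and Vz/F in SAP 3.1.3 so that the dose basis for each analyte is explicit.

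Add a programming check that CLu/F × AUC0-infu equals, for each subject and analyte, the dose used to compute CL/F.

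SAP 3.2.2.4.3, Table 14.2.3.2.3 and Listing 16.2.5.10.3 also plan unbound parameters for LP-951757, for which SAP 3.1.4 gives no formulas. Say in the same edit whether the corrected formulas apply there.

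The cost is two formulas, two lines of code and one check. No new data are needed and no inferential analysis changes.
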